### 5.1.2 Screening Visit

Prospective patients will be screened for eligibility up to 45 days prior to enrollment and the procedures will be performed as specified below. If convenient, the Screening and Baseline visits may be combined.

It is the investigator's responsibility to review the results of all laboratory tests as they become available. This review will be documented by the investigator's dated signature on the laboratory report. For each abnormal laboratory test result in which the value of the test lies outside the normal range (see [Appendix 2](#) for reference values), the investigator needs to ascertain if this is an abnormal (ie, clinically significant) result for the individual subject. The investigator may repeat the laboratory test or request additional tests to verify the results of the original laboratory

tests. If the laboratory value is determined by the investigator to be clinically significantly abnormal for that subject, the subject will be excluded from the study.

Records will be maintained of those individuals who are screened but do not meet the eligibility criteria for participation in the study.

- Informed consent and authorization
- Ophthalmic and medical history
- Concomitant medications and procedures
- Physical examination
- Pregnancy test (blood)
- Draw blood sample
- ECG
- Chest X-ray
- Visual acuity
- FFST (full field sensitivity test)
- Object detection and discrimination
- Complete ophthalmic examination
- IOP
- SD-OCT
- ERG
- AE review

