### 8.1 Definitions

#### 8.1.1 Adverse Event

An adverse event is any untoward medical occurrence in a subject or clinical investigation patient administered a pharmaceutical product and that does not necessarily have a causal relationship with this treatment. An adverse event can therefore be any unfavorable and unintended sign (including an abnormal laboratory finding), symptom, or disease temporally associated with the use of a medicinal (investigational) product, whether or not related to the medicinal (investigational) product. In addition, during the screening period, adverse events will be assessed regardless of the administration of a pharmaceutical product.

Note: Adverse events must be collected once informed consent has been obtained, regardless of whether or not the patient has been administered study treatment.

Progression of treatment indication including new or worsening of anticipated clinical signs or symptoms, which are collected as clinical efficacy variables and assessed as unequivocally associated with the disease progression and/or lack of efficacy, should NOT be reported as adverse events unless the disease progression is greater than anticipated in the natural course of the disease.

Adverse events will be assessed, documented, and recorded in the CRF throughout the study (ie, after informed consent has been obtained). At each visit, the investigator will begin by querying for adverse events by asking each patient a general, non-directed question such as “How have you been feeling since the last visit?” Directed questioning and examination will then be done as appropriate. All reported adverse events will be documented on the appropriate CRF.

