4.0 INTRODUCTION

This statistical analysis plan (SAP) provides a more technical and detailed elaboration of the statistical analyses of the safety and efficacy data as specified in the current protocol of Study RST-001-CP-0001 (amendment #2 dated 19 Oct 2017). Specifications of tables, figures, and data listings are contained in a separate document.

Study RST-001-CP-0001 is a Phase 1/2a, open-label, dose-escalation, non-randomized study of safety and tolerability of Intravitreal RST-001 in patients at least 18 years of age who have been diagnosed with advanced RP using criteria including clinical diagnosis, documented retinal electrophysiological evidence of rod-cone photoreceptor degeneration and baseline evidence of <10 microvolts (μ V) maximal b-wave electroretinography (ERG) response.

[figure not shown]
The length of this study participation will be 2 years with an additional 13 years of long-term follow-up.

Patients meeting the inclusion/exclusion criteria will receive a single 100 μ L intravitreal injection of RST-001 in the study eye. In Phase 1, three doses of RST-001 (low, mid and high), each group comprising of approximately but no less than three patients) will be evaluated by sequential dose escalation. In Phase 2a, up to 12 patients may be enrolled and receive RST-001 at the maximum tolerated dose. Patients who withdraw from the study prior to receiving the study treatment may be replaced.

The three doses of RST-001 are as follows:

	LOW Dose	MID Dose	HIGH Dose
RST-001	[REDACTED] vg/eye	[REDACTED] vg/eye	[REDACTED] vg/eye

The study design is shown graphically in Figure 4-1. The dose-escalation cohorts are illustrated in Table 4-1 below. The schedule of evaluations for Study RST-001-CP-0001 is presented in 2 and Table 4-3.

Figure 4–1. Overview of the Treatment Schedule**Table 4–2. Dose Escalation**

Phase	Group	Number of patients ^a	Intravitreal Injection	
			Vector concentration	Volume (µL)
1	A	3	LOW	100
	B	3	MID	100
	C	3	HIGH	100
2a		6-12 ^b	Choice of dose ^c from groups A, B, or C	100

^a Up to approximately 21 patients will be enrolled in this study.^b Number of patients is dependent upon whether or not the DSMC determines that, in their opinion, a treatment benefit for visual acuity/function has been observed in Phase 1.^c The maximum tolerated dose.

Table 4–3. Study Visit Schedule: Core Study Visits

	Screening ^b	Baseline ^b	Day			Month					
			0	1	7 ± 1	1 ± 7	3 ± 7	6 ± 7	9 ± 7	12 ± 30	18 ± 30

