11.1 ADVERSE EVENTS

Adverse events will be coded using *MedDRA*, version 21.0 or newer.

An AE will be considered a treatment-emergent adverse event (TEAE) if it was present after the first dose of study treatment or was present before the date of the first dose of study treatment and increased in severity after the first dose of study treatment. If more than 1 AE was reported before the first dose of study treatment and coded to the same preferred term, the AE with the greatest severity will be used for comparison with the AEs occurring during the reporting periods.

The number and percent of patients reporting TEAEs will be tabulated by treatment group in each phase separately during Core Study Visits and Long-term Follow-up Visits for the following categories:

- All TEAEs
- Treatment related TEAEs
- Ocular TEAEs in the study eye
- Non-ocular TEAEs
- Treatment-related ocular TEAEs
- Serious TEAEs
- Deaths
- AEs leading to study discontinuation

The above categories will also be tabulated by SOC and PT, or by PT only for ocular related categories, with the number and percentage of patients by treatment group in each phase and separately during Core Study Visits and Long-term Follow-up Visits, except for the last 3 categories.

In addition, the number and percent of patients will be tabulated by SOC, PT, and severity, or by PT and severity only for ocular related categories, with the number and percentage of patients by treatment group in each phase and separately during Core Study Visits and Long-term Follow-up Visits for the following categories:

- All TEAEs
- Treatment related TEAEs
- Ocular TEAEs in the study eye
- Non-ocular TEAEs
- Treatment-related ocular TEAEs

If more than 1 AE is coded to the same PT for the same patient, the patient will be counted only once for that PT using the greatest severity and strictest causality for the summarization by severity and causal relationship.

Separate tabular displays will be presented for patients who died, patients with SAEs, and patients with AEs leading to premature discontinuation.

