13.0 DETERMINATION OF SAMPLE SIZE

The sample size for this study was chosen empirically; no formal sample size computations to meet power requirements were made. The sample size of approximately 3 patients for each dose group in Phase 1 are typical for dose escalation studies, an additional up to approximately 12 patients will be enrolled in Phase 2a for further safety and efficacy evaluation.

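### The TEAE definition in SAP 11.1 tests presence after dosing, not onset, so read literally it also counts pre-injection AEs that continue unchanged

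*SAP*

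**What the plan says.** SAP 11.1 gives the only working definition. Its first limb reads: "An AE will be considered a treatment-emergent adverse event (TEAE) if it was present after the first dose of study treatment". The second limb, joined by *or*, covers an AE that "was present before the date of the first dose of study treatment and increased in severity after the first dose of study treatment". Where several pre-dose AEs share a preferred term, "the AE with the greatest severity will be used for comparison with the AEs occurring during the reporting periods". The resulting flag feeds the TEAE tables, which give numbers and percentages by treatment group within each phase.

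Protocol 11.3.3 refers to treatment-emergent AEs but does not define them. On collection, Protocol 8.1.1 states: "Adverse events must be collected once informed consent has been obtained, regardless of whether or not the patient has been administered study treatment". On timing, Protocol 5.1.2 states: "Prospective patients will be screened for eligibility up to 45 days prior to enrollment".

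On group size, SAP 13.0 states: "The sample size of approximately 3 patients for each dose group in Phase 1 are typical for dose escalation studies". SAP 4.0 states: "In Phase 2a, up to 12 patients may be enrolled and receive RST-001 at the maximum tolerated dose", and its dose-escalation table gives 6 to 12 patients for that phase.

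**The concern.** A treatment-emergent flag is meant to separate what appeared or got worse after dosing from what was already there. The first limb does not do this. It asks only whether the AE was present after the dose, and an AE that started during screening and persists at the same severity meets that test.

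The wording also undoes the rest of the rule. An AE that worsens after dosing is necessarily present after dosing, so the second limb adds no case. For the same reason, comparison with the worst pre-dose severity cannot change any flag.

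The documents leave room for such events. AEs are recorded from consent. Protocol 8.1.4 provides for AEs related to diagnostic procedures in the screening and baseline period. Protocol 3.11.1.3 names corneal abrasion from the ERG contact lens as a risk, and ERG is a screening test. An ocular AE of that kind in the study eye, still present after injection, would be tabulated as an ocular TEAE. In dose groups of about three, one such patient is visible in the percentages.

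**Working it through.** **Inputs**

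- First limb: AE present after the first dose (SAP 11.1). Call this *post*.
- Second limb: AE present before the first dose and more severe after it (SAP 11.1). Call these *pre* and *worse*.
- Pre-dose collection: from consent (Protocol 8.1.1), with screening at most 45 days before enrollment (Protocol 5.1.2).
- Group sizes: about 3 per Phase 1 dose group (SAP 13.0) and 6 to 12 in Phase 2a (SAP 4.0). Check: 3 × 3 + 12 = 21, which agrees with the stated maximum of approximately 21.
- Not in the documents, so assumed: q, the share of patients with an unchanged ongoing pre-injection AE, 5% to 30%; and p, the share with at least one genuine TEAE, 20% to 80%.

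The plan states no TEAE rate, power or error level that bears on this, so there is no figure to reproduce.

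**Step 1: compare the two rules**

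Literal rule: *post* OR (*pre* AND *worse*). New-or-worsened rule: (*post* AND NOT *pre*) OR (*pre* AND *worse*).

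| pre | post | worse | literal | new-or-worsened |
|---|---|---|---|---|
| no | no | no | not TEAE | not TEAE |
| no | yes | no | TEAE | TEAE |
| yes | no | no | not TEAE | not TEAE |
| yes | yes | no | **TEAE** | **not TEAE** |
| yes | yes | yes | TEAE | TEAE |

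The rules differ in exactly one case: present before, present after, not worsened.

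**Step 2: look for text that repairs it**

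- SAP 15.6 (missing severity) and 15.7 (missing causality) depend on whether the AE started before, or on or after, the first-dose date. They only fill in missing values.
- SAP 15.8 imputes incomplete start dates. It does not remove an AE with a known pre-dose start.
- Protocol 11.3.3 leaves the term undefined.

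None of these excludes the case in Step 1.

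**Step 3: size per affected patient**

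One extra patient in a row adds 1/n: 1/3 = 33.3 points, 1/6 = 16.7 points, 1/12 = 8.3 points. A preferred-term row moves only if that patient has no genuine TEAE of the same term. The any-TEAE row moves only if the patient has no other TEAE at all.

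**Step 4: chance that a group contains at least one such patient**

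Formula: 1 − (1 − q)^n, treating patients as independent. For example, with q = 10% and n = 3, 1 − 0.9³ = 27.1%.

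| q (assumed) | n = 3 | n = 6 | n = 12 | all 9 in Phase 1 |
|---|---|---|---|---|
| 5% | 14.3% | 26.5% | 46.0% | 37.0% |
| 10% | 27.1% | 46.9% | 71.8% | 61.3% |
| 20% | 48.8% | 73.8% | 93.1% | 86.6% |
| 30% | 65.7% | 88.2% | 98.6% | 96.0% |

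**Step 5: expected effect on the any-TEAE row**

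If the two kinds of event are independent, literal incidence is p + q − pq, so the excess is (1 − p)q.

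- p = 20%: 8 points at q = 10%, 16 points at q = 20%.
- p = 50%: 5 and 10 points.
- p = 80%: 2 and 4 points.

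Across 21 patients with p = 80%, that is 21 × 0.02 = 0.42 to 21 × 0.04 = 0.84 expected extra patients.

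**The case against.** The strongest reply is that the intent is recoverable. The worsening limb and the severity comparator make sense only under a new-or-worsened rule, and SAP 15.6 and 15.7 already use onset language. A programmer may well implement the intended rule. The table specifications are in a separate document that is not available here, so the documents do not show that any table will be wrong. That stands. It limits the claim to what the text says if followed, but it does not correct the text: the definition in the SAP is the operative rule and should not depend on a reader overriding it.

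The reply also limits the size of the effect. A reader might infer that any-TEAE incidence in a group goes from 0% to 33%. That requires that nobody in the group has any other TEAE. Protocol 6.2.2 describes mild conjunctival hyperemia and subconjunctival hemorrhage as common after the injection that every patient receives, and core follow-up lasts 24 months, so a starting point of 0% is unlikely.

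A reader might also take an assumed 10% to 20% of 21 patients (2.1 to 4.2) as patients added to the count. That figure is the number who carry such an AE. The number added is smaller wherever those patients have other TEAEs, as Step 5 shows, and the 10% to 20% has no source in the documents.

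Nor do the documents show that such AEs will occur, only that they can. The 45 days is a maximum, Screening and Baseline may be combined, and SAP 11.9.1 sends screening physical-examination findings to medical history.

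**Conclusion.** The definition is wrong as written, and the SAP should be corrected. On its literal terms it counts a pre-injection AE that continues unchanged, and it leaves its own second limb and comparator without function. No other text in either document repairs this.

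The effect is mainly on preferred-term rows: 33 points per affected patient in a group of 3, 17 in 6 and 8 in 12, subject to the overlap conditions in Step 3. How many patients would be affected cannot be determined from the documents; the probabilities in Step 4 depend entirely on the assumed q and on independence.

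A reader might infer that the trial's safety conclusion is at risk. The documents do not support that. The primary criterion, the absence of a related AE of grade 3 or higher (SAP 5.0), does not use the flag, and neither do the enrollment stopping rules or the dose-limiting toxicity definition (Protocol 7.4). Treatment-related rows are largely protected, since SAP 15.7 imputes a causal link only for AEs that start on or after the first-dose date. The error would over-count events; it would not hide harm.

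**What to change.** Replace the defining sentence in SAP 11.1 with wording to this effect:

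*An AE is treatment-emergent if its onset is on or after the date of the first dose, or if it was already present before the first dose and became more severe after it. A Day 0 onset that cannot be placed before the injection counts as treatment-emergent.*

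Keep the existing comparator rule, which then has its intended function.

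Anchoring on the date matches SAP 15.6 and 15.7. The Day 0 default is needed because the documents do not show that AE onset time is collected, and SAP 15.8 assigns the first-dose date to some incomplete start dates. A rule that required onset time for every Day 0 event could not classify those records.

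The cost is one SAP sentence, plus a check that the table specifications and flag programming agree with it. No new data are needed. Protocol 11.3.6 has the analysis plan finalized before database lock, so the edit belongs in the SAP before then.

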11.2 PRIMARY OCULAR SAFETY MEASUREMENTS

The following visual function measures at 6 months are considered primary safety endpoints. They will be listed and summarized by treatment group separately in each phase.

- Change from baseline in visual acuity in the study eye
- Change from baseline in full field sensitivity in the study
- Change from baseline in ambulation
- IOP measurements in the study eye
- Changes from baseline in anatomical parameters as measured in the study eye by:
 - Fundus photography - Qualitative assessment of the retinal appearance
 - Spectral domain-OCT (SD-OCT) - Qualitative assessment of the retinal cross-sectional appearance

11.3 SECONDARY OCULAR SAFETY MEASUREMENTS

The following ocular safety measures (excluding the primary safety endpoints at 6 months as described in Section 11.2) and their change from baseline values will be listed and summarized by visit and by treatment group separately in each phase. Data collected from the extended follow-up will be included in data listings.

- Change in visual acuity in the study eye from Baseline (defined as last observed value prior to dosing) to [REDACTED]
- Change in full field sensitivity in the study eye from Baseline to [REDACTED]
[REDACTED]
- Change in ambulation scores from Baseline to [REDACTED]
- Change in object detection and discrimination scores from Baseline to [REDACTED]
[REDACTED]
- Change in VEP and ERG scores from Baseline to [REDACTED]
- Anatomical parameters as measured in the study eye by:
 - Fundus photography - Qualitative assessment of the change in retinal appearance from Baseline to [REDACTED]
 - Spectral domain-OCT (SD-OCT) - Qualitative assessment of the change in retinal cross-sectional appearance from Baseline to [REDACTED]
[REDACTED]

11.4 OTHER OCULAR SAFETY MEASUREMENTS

Other ocular safety measurements include the following assessments during the core study visits and clinic visits of the long-term follow-up visits:

- IOP measurements in the study eye (other assessment at month 6 which is the primary endpoint)
- Findings in the study eye from ocular biomicroscopic examination (Table 11.4-1)
- Findings in the study eye from ophthalmoscopy examination (Table 11.4-2)

Table 11.4–1. Findings and Severity from Ocular Biomicroscopic Examination

Biomicroscopic Eye Area	Findings	Severity^a
Eyelids/eyelid margins/lashes	Erythema Edema Crusting Other	+0.5 (Trace) +1 (Mild) +2 (Moderate) +3 (Severe) Not Applicable
Conjunctiva (bulbar or palpebral)	Hyperemia Edema Subconjunctival Hemorrhage Discharge Blanching Follicles Pterygium, encroaching on visual axis Pterygium, not encroaching on visual axis Other	+0.5 (Trace) +1 (Mild) +2 (Moderate) +3 (Severe) Not Applicable
Cornea: • Central Cornea • Peripheral Cornea • Central and Peripheral Cornea	Punctate Epithelial Staining Filaments Infiltrates Edema Corneal Guttata Endothelial Pigment Keratic Precipitates Neovascularization Opacity/Opacities Stromal Haze Other	+0.5 (Trace) +1 (Mild) +2 (Moderate) +3 (Severe) Not Applicable
Anterior chamber	Cells Flare Anterior Synechiae Hypopyon, Details and Levels (mm) Hyphema, Details and Levels (mm) Other	0 (<1 cell, None) +0.5 (1-5) +1 (6-15, Faint) +2 (16-25, Moderate) +3 (26-50, Marked) +4 (>50, Intense (including fibrin)) Not Applicable
Iris/pupil	Rubeosis Iridis, anterior chamber angle involved Rubeosis Iridis, anterior chamber angle not involved Afferent Pupillary Defect (APD) Other	Not Applicable

^aSeverity for Anterior chamber cells and flare are included before or after '/', respectively.

Table 11.4–2. Findings and Severity from Ophthalmoscopy Examination

Ophthalmoscopy Eye Area	Findings	Severity^a
Optic Nerve	Cup/Disc Ratio (Value range 0.0 - 1.0)	Not Applicable
Vitreous	Cells Vitreous Haze Vitreous Hemorrhage Posterior Vitreous Detachment Other	+0.5 (None, No Haze) +1 (Minimal, Trace) +2 (Mild, 1+) +3 (Moderate, 2+) +4 (Marked, 3+) +5 (Severe, 4+) Not Evaluable Not Applicable
Optic Nerve	Disc Hemorrhage Other	Not Applicable
Macula	Intraretinal Fluid Subretinal Fluid Intraretinal Hemorrhage Subretinal Hemorrhage Rhegmatogenous Detachment Tractional Detachment Pigment Epithelial Detachment Other	Not Applicable
Fundus	Other	Not Applicable
Retina Periphery	Retinal Hemorrhage Retinal Tear Rhegmatogenous retinal detachment, macula center attached Rhegmatogenous retinal detachment, macula center detached Tractional retinal detachment, macula center attached [Tractional retinal detachment, macula center detached Exudative retinal detachment, macula center attached Exudative retinal detachment, macula center detached Other retinal detachment Round (Atrophic) Retinal Hole Lattice Degeneration Other	Not Applicable

^aSeverity for Vitreous flare and Vitreous Haze are included before or after ' ; ' , respectively.

The findings from both ocular biomicroscopic and ophthalmoscopy examinations with prespecified terms will be coded using MedDRA, version 21.0 or newer.

Descriptive statistics for IOP measurements and changes from the baseline values at each visit will be presented by treatment group separately for each phase.

Similarly, descriptive statistics for cup/disc ratio measurements from ophthalmoscopy examination and changes from the baseline values at each visit will be presented by treatment group separately for each phase.

The number and percent of patients with more than one grade increase from baseline for any findings will be summarized by preferred term and by treatment group separately for each phase.

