#### **3.6.2.1 Dog Study**

The dog study was conducted in healthy male and female animals 5-6 months of age. The dog was chosen as the animal model for this study as it is an accepted non-rodent species for preclinical ocular toxicity testing by regulatory agencies. There were 8 dogs per dose group and 4 dose groups. Actual doses verified were vehicle (control); [REDACTED] (Low), [REDACTED] (Mid), and [REDACTED] (High) vg/eye of RST-001. Two dogs/sex/time point were administered, in the right eye, a single- [REDACTED]  $\mu$ L intravitreal injection of vehicle or RST-001. Animals were sacrificed on Day 36 and Day 99.

No noteworthy adverse effects were observed in the body weight, food consumption, clinical pathology or organ weights following administration of RST-001 at any dose level.

RST-001-related findings, consisting of ocular inflammation, were observed beginning at least 5 weeks after administration with an increasing incidence and severity with dose at all dose levels. Ophthalmic findings of anterior uveitis (anterior chamber cells, keratic precipitates and/or cell-like deposits on the corneal endothelium) were observed at Week 5 in 8/8 high dose eyes and 3/8 or 1/8 eyes for the mid and low doses, respectively. During the recovery period, findings generally remained stable or progressed. Findings related to chronic inflammation, including the presence of perivasculär retinal opacities in addition to findings in the anterior chamber, were present at all dose levels at the end of the recovery period. In 2/8 high dose animals, the level of inflammation was greater when compared to other animals and was accompanied by anterior chamber flare, fibrin, corneal edema, pupil incomplete dilation, fundus hazy view, corneal vessels and/or lens opacities. These observations correlated with microscopic

findings. At the high dose, these consisted of minimal to marked mixed cell (lymphocytes, macrophages, and rarely, neutrophils) inflammation of the anterior chamber (iridocorneal angle), iris, ciliary body, vitreous body and/or retina. At the mid and low dose, findings were limited to minimal to mild cell inflammation in the ciliary body, vitreous body and/or iris. There were no signs of overt tissue damage due to direct toxicity of the test item and no cellular or humoral immune response to RST-001 was detected at any dose level.

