### **5.2.15 Complete Ophthalmic Examination**

A complete ophthalmic examination will be performed in both eyes at the Screening and Baseline visits and at each visit after study treatment administration. The examination will include a slit lamp biomicroscopic evaluation of the conjunctiva, cornea, anterior chamber, iris, and lens. The posterior segment and fundus will also be evaluated through dilated pupils by indirect ophthalmoscopy. Intraocular pressure will be measured using Goldmann applanation tonometry or a hand held tonometer (using the same instrument for each patient throughout the study, when possible). If Goldmann applanation tonometry is used to measure IOP, then it must be performed after fundus photography and autofluorescence to prevent fluorescein dye from interfering with the images.

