### 6.1.1.2 Ocular Inflammation

Owing to the potential for intraocular inflammation (as noted in the preclinical dog study) or immunogenicity, signs of ocular inflammation will be carefully monitored throughout the study and reported to the DSMC. Active inflammation of the anterior chamber, vitreous and retina/choroid will be documented in the case report forms according to recognized international criteria shown in [Table 4](#), below. Additional investigations, such as OCT and fluorescein angiography, may be performed at the discretion of the investigator according to clinical findings and accepted standards of care.

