### **6.2.1        Intraocular Inflammation and Immunogenicity Related to RST-001**

During the study, evidence of immune response to RST-001 will be monitored by systemic measurement of humoral and cellular immunity as follows:

These tests will be performed at several timepoints during the study:

There is no diagnostic test available for ocular immunogenicity. Instead, clinical evidence suggestive of immunogenicity will be gathered. Examination findings such as reduced visual acuity in the study eye, intraocular inflammation, uveitis, retinal vasculitis, retinal edema, hemorrhage, exudation and/or detachment will also be gathered. Additional evaluations such as OCT and fluorescein angiography may also aid the clinical identification of an immune response.

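### The SAP's eye-examination tables have no lens row and no retinal inflammation entry, so neither kind of finding can appear in the exam-based summaries by dose

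*SAP*

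**What the plan says.** **What is examined and recorded.** Protocol 5.2.15 specifies, in both eyes and at each visit after treatment, "a slit lamp biomicroscopic evaluation of the conjunctiva, cornea, anterior chamber, iris, and lens", followed by dilated ophthalmoscopy. Protocol 6.1.1.2 adds: "Active inflammation of the anterior chamber, vitreous and retina/choroid will be documented in the case report forms". Protocol 6.2.1 lists the clinical signs that would suggest immunogenicity; among them, "retinal vasculitis, retinal edema, hemorrhage, exudation and/or detachment will also be gathered".

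**What the dogs showed.** Protocol 3.6.2.1 reports perivascular retinal opacities which, with other signs of chronic inflammation, "were present at all dose levels at the end of the recovery period". In 2 of 8 high-dose animals the inflammation was more marked, and the accompanying signs included "fundus hazy view, corneal vessels and/or lens opacities".

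**What is analysed.** SAP 11.4 gives two lists of findings for the study eye. Table 11.4-1 (slit lamp) covers eyelids, conjunctiva, cornea, anterior chamber and iris/pupil. Table 11.4-2 (ophthalmoscopy) covers optic nerve, vitreous, macula, fundus and retina periphery. On coding, the SAP states: "The findings from both ocular biomicroscopic and ophthalmoscopy examinations with prespecified terms will be coded using MedDRA, version 21.0 or newer". Apart from IOP and cup/disc ratio, section 11.4 plans one summary: the number and percent of patients whose grade for a finding rose by more than one step from baseline, by preferred term, dose group and phase.

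**The concern.** The protocol gives the preclinical dog inflammation as a reason for watching the eye closely. The examination tables are where a systematic record, made at every visit in every treated eye, becomes an incidence by dose. Two of the dog findings, lens opacity and perivascular retinal opacity, have no entry there. A reader of those tables would see nothing under either heading at any dose, and could not tell whether the finding was absent or simply not tabulated.

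This matters most late in the study. At Months 36, 48 and 60 (protocol 5.1.14) the complete ophthalmic examination is the only scheduled structural assessment of the eye, because fundus photography and SD-OCT are not among the procedures at those visits. In the dogs, findings generally persisted or worsened over the recovery period.

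**Working it through.** The plan states no figure to reproduce; SAP 13.0 says that "no formal sample size computations to meet power requirements were made". The check is a comparison of texts, followed by simple arithmetic for size.

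**Step 1. Slit-lamp structures.** Protocol 5.2.15 names five: conjunctiva, cornea, anterior chamber, iris and lens. Table 11.4-1 has rows for the first four (plus eyelids) and none for the lens. Coverage is 4 of 5. The lens lacks even an 'Other' field, and the only opacity entry in the table sits under the cornea. Table 11.4-2 has no lens row either.

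**Step 2. Retinal and choroidal inflammation.** Protocol 6.1.1.2 refers to protocol Table 4 for grading, but Table 4 grades only anterior chamber cells, flare and vitreous haze. In SAP Table 11.4-2 the macula row lists fluid, hemorrhage and detachments; the fundus row holds only 'Other'; the retina periphery row lists hemorrhage, tear, detachments, hole and lattice degeneration, then 'Other'. None of the named entries is vasculitis, perivascular change or chorioretinal inflammation. Retinal fluid, hemorrhage and detachment (including exudative detachment) from the protocol 6.2.1 list are covered.

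**Step 3. Dog findings against the SAP lists.**

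| Dog finding | SAP entry |
|---|---|
| Anterior chamber cells, flare | Yes |
| Fibrin | Yes, as flare grade 4 |
| Keratic precipitates | Yes |
| Corneal edema, corneal vessels | Yes (edema, neovascularization) |
| Endothelial deposits | Approximate (endothelial pigment, keratic precipitates) |
| Hazy fundus view | Approximate (vitreous haze) |
| Perivascular retinal opacities | None; 'Other' under macula, fundus or periphery |
| Lens opacities | None, and no row |
| Incomplete pupil dilation | None; not pursued here |

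**Step 4. Apply the summary rule.** To be counted, a finding needs (a) a preferred term and (b) a severity scale on which it can rise by more than one grade.

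- *Lens opacity:* there is no row, so neither (a) nor (b) is met.
- *Perivascular opacity or vasculitis entered as 'Other':* the SAP provides for no coding, so (a) is not met as written. Severity for the macula, fundus and periphery rows is 'Not Applicable', so (b) is not met either.
- *Test of (b) alone:* retinal detachment is prespecified and would be coded, yet it also carries 'Not Applicable' and so cannot enter the summary. Adding terms without changing the summary would therefore leave retinal findings uncounted.

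**Step 5. Size of one uncounted case.** One case in a group of n is 100/n percentage points of that group's incidence.

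- Phase 1, n = 3: 100/3 = 33.3 points.
- Phase 2a, n = 6: 100/6 = 16.7 points.
- Phase 2a, n = 12: 100/12 = 8.3 points.

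**The case against.** The strongest reply is that nothing need be lost overall, because other routes exist.

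- *Adverse events.* Under protocol 8.1.1 a new cataract or retinal vasculitis is an unfavorable sign and so qualifies as an AE. SAP 11.1 codes all AEs and tabulates ocular TEAEs in the study eye by preferred term and by severity, per dose group and phase. This stands, and a case reported this way loses nothing from incidence. But it depends on the investigator deciding to report the examination finding as an AE, a step that systematic exam summaries do not need.
- *Imaging.* Fundus photography and SD-OCT are summarized at Month 6 (SAP 11.2) and at further times (SAP 11.3). This stands for the retina, although the assessment is qualitative with no stated categories. It does not cover the lens.
- *Listings and the DSMC.* SAP 15.4 lists all assessments, and protocol 6.1.1.2 has signs of ocular inflammation reported to the DSMC. With about 3 patients per dose group, individual cases can be read from a listing. A listing still gives no incidence by dose.
- *Unseen documents.* Table specifications are in a separate document, and the eCRF is not available here. Either could close part of the gap.

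Four stronger readings are tempting but not supported. A reader might infer that such an event never reaches any table; the TEAE and imaging routes show otherwise. A reader might infer that the SAP forbids coding of 'Other' text; it is merely silent. A reader might call these injuries, or expected toxicities of the product; the dog report describes inflammation without overt tissue damage from direct toxicity, protocol 3.11.1.2 says that the risks are not known, and lens opacity was one item in an and/or list for 2 of 8 animals. Finally, a new lens opacity could affect visual function measures, but the documents give no basis for saying that it would bias the efficacy results or by how much.

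**Conclusion.** The gap is real and limited to the exam-based summaries. As SAP 11.4 is written, a new lens opacity or a retinal inflammatory finding cannot be counted there at any dose, although the protocol requires the lens to be examined and the retinal signs to be recorded. For the retina there are two separate causes, the missing terms and the absence of any grade, and the second holds even if 'Other' text is coded.

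The size is one case at a time: about 33 percentage points in a Phase 1 group of 3, and about 8 to 17 points in Phase 2a. These figures assume that the case is not captured as a TEAE or, for the retina, through imaging.

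The primary safety criterion, absence of related AEs of grade 3 or higher, runs through AE reporting and not through these tables. This is an inexpensive improvement worth making, not a flaw that undermines the trial. It assumes that the unseen table specifications and eCRF do not already supply the missing entries.

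**What to change.** In SAP 11.4:

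1. Add a lens row to Table 11.4-1, with lens status and new or worsened opacity.
2. Add retinal vasculitis/perivascular opacity and chorioretinal inflammatory lesion to Table 11.4-2.
3. State that 'Other' free text is coded to MedDRA.
4. Tabulate, by dose group and phase, the number and percent of study eyes with each finding absent at baseline and present afterwards. For a lens opacity already present at baseline, also count worsening. This item is essential, because ungraded findings cannot enter a summary of grade increases.

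The cost is some coding work and possibly a small eCRF change; if the form has no lens field, that has to be settled first. The examinations are already scheduled. The SAP is written to Amendment 2, while the current protocol's interim analysis section (11.3.6) allows the plan to be finalized up to database lock, so the change can go into the revision that is needed in any case.
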